8.2 ANALYSIS VARIABLES

The primary analysis variable is proportion of live born infants with a major structural birth defect within the first year of life and the secondary analysis variables: proportion of major structural defects in all pregnancies, proportion of infants with a pattern of 3 or more specific minor anomalies, the incidence of spontaneous abortion; stillbirth; preterm delivery; small-for-gestational age on birth weight, length, head circumference; small for age at 1 year follow-up on weight, length or head circumference.

Additional analysis variables that may or may not be included as important confounders or in sub-analyses include but are not limited to the following:

- Maternal age
- Maternal race/ethnicity
- Socioeconomic status
- Prior pregnancy history: gravidity/parity and previous outcomes
- Periconceptional use of folic acid containing supplements
- Unintended pregnancy
- Gestational age at enrollment
- Exposure to other medications (including known teratogens) and other MS medications
- Comorbidities
- Disease severity measure (s)
- Dose and gestational timing of exposure to teriflunomide
- Gestational timing and course of cholestyramine elimination
- Blood levels of teriflunomide if performed in pregnancy

8.2.1 Main criteria

The primary interest is the birth prevalence of major structural defects, in the first year of life, in the teriflunomide-exposed group.

As defined in [Section 7.2.3.3](#), a major structural defect is defined as a defect which occurs in less than 4 percent of the population and which has either cosmetic or functional significance to the child (e.g., a cleft lip). The CDC's MACDP coding manual for major structural defects will be used as a guide for categorization of such defects.

The primary comparison group is the MS disease-matched Cohort II. The secondary comparison group is Cohort III. The additional external comparison will be made to the MACDP birth defects rate.

8.2.2 Other criteria

Other interests are the major structural defects in all pregnancies (refer to [Section 7.2.3.3](#) for definition), the prevalence of a specific pattern of 3 or more minor structural defects in the live born infants who receive the dysmorphological examination, the incidence of spontaneous abortion; stillbirth; preterm delivery; small-for-gestational age on birth weight, length, head circumference; small for age at 1 year follow-up on weight, length or head circumference.

A pattern of 3 or more minor malformations is defined as any 2 or more infants in the teriflunomide-exposed group who have the same 3 or more specific minor structural defects. Should a pattern exist, comparison would be made to the number of infants, if any, in the comparison group who have the same pattern of 3 or more specific minor structural defects.

The primary comparison group for these outcomes is also the MS disease-matched comparison group Cohort II. The secondary comparison group is Cohort III.

8.3 STATISTICAL METHODS

8.3.1 Primary endpoint

The primary endpoint is rate of major structural defects in live born infants. Due to the expected low incidences of major defects, diagnosed within the first year of life, the primary comparison will be carried out using Fisher's exact test between the teriflunomide-exposed group (Cohort I) and the disease-matched comparison group (Cohort II). Although Cohort II is "matched" to Cohort I on the underlying maternal diagnosis of MS, no a priori matching on disease severity is performed at the time of recruitment. Therefore, measures of MS severity will be addressed as confounders in the analyses comparing Cohort I to Cohort II as described below.

Due to the observational nature of the study, it is necessary to adjust for confounders to address baseline differences between the teriflunomide exposed and the comparison groups.

Ensure that the printed copy of this document is the current version available on the Intranet.

The potential confounders to be evaluated will be those itemized in the analysis variables in [Section 8.2](#) (e.g., maternal age, MS severity). Confounders will be those variables that modify the odds ratio for the outcome by at least 10% in logistic regression with exposure to teriflunomide and the potential confounder as predictors. In addition, any variable that is deemed to be clinically relevant will be considered for inclusion in multivariate analysis even if the 10% criterion is not met. The adjustment for confounders will be carried out using logistic regression, the primary outcome variable as the dependent variable, and with confounders included in the models as independent variables adjusting for the effect of exposure. Stepwise procedures will be used in case of many identified confounders, as sample size permits. Propensity scoring methods will be considered. The analysis of major birth defects will be further stratified based on prenatal diagnosis performed prior to enrollment or not.

Secondary comparisons will be made between the teriflunomide exposed group (Cohort I) and the healthy comparison group (Cohort III). The rate of major structural defects will also be compared to the most recently available rate from the MACDP.

8.3.2 Secondary endpoints

The secondary endpoints of this study include: proportion of major structural defects in all pregnancies excluding lost-to-follow-up, prevalence of a specific pattern of 3 or more minor structural defects in the live born infants who receive the dysmorphological examination, rates of spontaneous abortion, preterm delivery, proportion of live born infants who are small for gestational age (less than or equal to 10th percentile for gestational age and sex) on weight, length or head circumference, and proportion of infants less than or equal to the 10th percentile for sex and age on weight, length or head circumference at 1 year postnatal evaluation. The above endpoints, other than spontaneous abortion and preterm delivery, are binary and will be analyzed in the same fashion as major structural defects, with the exception that the Chi-squared test will be used for comparison between the exposed and the comparison group when the events are not rare. For spontaneous abortion and preterm delivery, survival analyses incorporating left truncation for spontaneous abortion (women may enroll in the study any time between 0 to 20 weeks of gestational age) and right censoring when the subject is no longer at risk of the event are conducted. The comparison between the exposed and the comparison group will be carried out using log-rank test, and confounders will be adjusted using the Cox proportional hazards regression model.

For all endpoints, exposure effect will also be investigated using the timing and dose of exposure, in a fashion similar to using the group indicator as above.

Also influencing fetal exposure is the success of the cholestyramine elimination procedure. Therefore, detailed data on the dose, gestational timing of the elimination procedure (s) and adherence to the guidelines for drug elimination procedure will be incorporated into the analysis of exposure in relation to outcome, and these maternally collected data will be supplemented by medical records and blood levels as available.

CSD-003149 VERSION N°1.0 (20-JUL-2010)

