7.2.3 Data Collected from medical records

Medical records from the prenatal care provider, the hospital of delivery, the neurologist, the pediatrician, and any other specialty provider such as a pathologist, if relevant, will be examined for additional exposure and outcome data. Upon completion of the outcome interview, regardless of the outcome of the pregnancy, each woman will be mailed a packet containing medical records release forms for the delivery hospital, obstetrician, pediatrician, and neurologist if applicable, as well as the laboratory results, if blood levels of teriflunomide were obtained at any time point during or just prior to pregnancy and documentation of courses and dates of the drug elimination procedure. Each woman will be asked to sign the medical records release forms and to return them along with the pregnancy exposure diary form.

Upon receipt of the signed medical records release forms, a standard physical evaluation form will be mailed to the physician responsible for the care of each live born infant at or near 1 year of age. This form includes information on infant size at the time of the latest examination and an open-ended question about postnatal complications and congenital anomalies.

Data abstracted from the medical records include the following:

- Prenatal tests and results
- Measures of disease activity/severity during pregnancy, age at diagnosis
- Blood levels of teriflunomide and dates measured (if available)
- Courses of cholestyramine or charcoal prescribed and dates
- Outcome of pregnancy
- Gestational age at pregnancy end
- Sex of the infant (s)
- Delivery type
- Type of hospital stay
- Maternal and infant complications

- Maternal weight gain, pre-pregnancy body mass index
- Major structural defects, and any diagnostic tests to confirm
- Birth weight, length, head circumference
- Postnatal weight, length, head circumference
- Apgar scores
- Method of infant feeding
- Pathology results, if relevant, e.g., for stillbirths

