7.2.3.4 Outcome classification for secondary endpoints for cohort study

- Pattern of minor structural defects is defined as any 2 or more infants receiving the study dysmorphology examination in the teriflunomide-exposed cohort (Cohort I) who have the same 3 or more minor structural defects. If a pattern or patterns are identified, the prevalence of the same pattern in Cohorts II and III is evaluated.
- Spontaneous abortion: spontaneous abortion is defined as non-deliberate fetal death which occurs prior to 20 completed week's post-LMP.
- Elective abortion: elective abortion is defined as deliberate termination of pregnancy at any time in gestation.
- Stillbirth: stillbirth is defined as non-deliberate fetal death anytime in gestation at or after 20 completed week's post-LMP.
- Premature delivery: premature delivery is defined as live birth prior to 37 completed weeks gestation as counted from LMP (or calculated from first-trimester ultrasound-derived due date if last menstrual period uncertain or more than 1 week discrepant).

CSD-003149 VERSION N°1.0 (20-JUL-2010)

Ensure that the printed copy of this document is the current version available on the Intranet.

Elective cesarean deliveries or inductions prior to 37 completed weeks will be considered separately.

- Small for gestational age: small for gestational age is defined as birth size (weight, length or head circumference) less than or equal to the 10th percentile for sex and gestational age using National Center for Health Statistic (NCHS) pediatric growth curves for full term infants. Prenatal growth curves will be used for premature infants.
- Postnatal growth deficiency up to 1 year of age: postnatal growth deficiency is defined as postnatal size (weight, length or head circumference) less than or equal to the 10th percentile for sex and age using NCHS pediatric growth curves, and adjusted postnatal age for premature infants.
- Lost-to-follow-up: Subjects will be considered lost-to-follow-up if they have completed the initial intake interview but subsequently fail to complete the outcome interview and medical records release despite a standard number of telephone attempts and attempt to contact by mail as per study procedure manual within 1 year of the mother's estimated due date. Voluntary subject withdrawals will be considered separately.

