8.4 DETERMINATION OF SAMPLE SIZE

Based on previous experience with the OTIS Autoimmune Diseases in Pregnancy Project, it is estimated that subjects will be an average of 6-9 weeks post-LMP at the time of enrollment. Given this mean gestational timing at enrollment, the anticipated spontaneous abortion and stillbirth rate is 10%, the estimated elective abortion rate is <2%, the estimated lost-to-follow-up rate is 4% (based on previous OTIS experience) resulting in approximately 64 live born infants from a total of 75 enrolled in the teriflunomide-exposed group and 106 live born infants in each comparison group from a total of 125 enrolled in each group at the end of 5 years of recruitment. Experience with the current OTIS Autoimmune Diseases in Pregnancy Project has demonstrated a yield of approximately 90% live born infants from the total proportion enrolled. Therefore, the estimated yield of 85% in this proposal is conservative. We estimate baseline rates of major structural defects, spontaneous abortion, premature delivery, and small for gestational age based on previous OTIS studies and on general population data. With this sample size, at 80% power and 2-sided significance level of 0.05, using Fisher's exact test we will be able to detect a relative risk of 5.57 for proportion of major structural defects in the teriflunomide exposed group versus the diseased matched comparison group, which has an assumed major structural defect rate of 3%, which is the background rate of the external comparison group (MACDP). There is no evidence of an increased risk of major structural defects in general in women with MS. The following table also provides the type of differences that can be detected between the primary comparison groups for a pattern of minor malformation, spontaneous abortion, preterm delivery, and small for gestational age, given the baseline rates assumed in the comparison group, with at

Ensure that the printed copy of this document is the current version available on the Intranet.

least 80% power and 2-sided significance level of 0.05, under the sample size, except as otherwise noted(13).

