The sample size selected and the associated detectable relative risk is due to the relative rarity of expected exposures given the Pregnancy Category X designation and the extensive efforts by health-care providers and women to avoid pregnancy exposures. The sample size and detectable relative risk could only be increased by failure of pregnancy prevention efforts. However, the strength of the proposed approach, despite small sample size, is the high level of scrutiny of exposed pregnancy outcomes with dysmorphological exams (at the same level in controls) in terms of detecting any pattern of malformation and/or any consistency with malformations reported in animal data.

Table 3 - Sample Size and Detectable Effect Size

Outcome	Sample Size Exposed Cohort I: Comparison Cohort II	Baseline Rate in Disease-Matched Comparison Cohort II	RR or % in Exposed*
Major Structural Defects	64:106	3%	5.57
Specific Pattern of 3 or more minor structural defects	64:106	0%	8.5%
Spontaneous Abortion	75:125	10%	2.55
Premature Delivery	64:106	6%	3.50
SGA Small for Gestational Age	64:106	10%	2.68

*Fisher's exact test for major structural defects; one-tailed Fisher's exact test for pattern of minor structural defects; chi-square test for all other outcomes

For the comparison of a specific pattern of 3 or more minor structural defects, the pattern itself must be comprised of at least 2 infants in the exposed group who have the same 3 defects, and this is compared to the incidence of that same pattern in the comparison group; therefore a 1-tailed test is used, and the estimate of the incidence in the comparison group is 0. The sample size is sufficient to detect an incidence rate of 8.5% of a specific pattern in the exposed group (or approximately 5 children) which is comparable to the 10% incidence of a specific pattern of minor structural defects associated with other known human teratogens of moderate risk such as anticonvulsant medications.

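### Birth size and 1-year size are measured on a scale but analysed only as at or below the 10th percentile; an adjusted z-score analysis alongside would add power if exposure shifts size across the whole cohort

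*Protocol*

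**What the plan says.** Protocol section 4.2 names small for gestational age, at birth and at the 1-year follow-up, among the secondary outcomes. Section 7.2.3.4 defines both outcomes by a percentile cut on any of three measures. For 1-year size the text is "postnatal growth deficiency is defined as postnatal size (weight, length or head circumference) less than or equal to the 10th percentile for sex and age", and the birth definition has the same form for sex and gestational age.

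The underlying data are measurements. Section 7.2.3 abstracts birth weight, length and head circumference from the records, and also "Postnatal weight, length, head circumference". The dysmorphology examination (section 7.2.3.1) adds length and head circumference.

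Section 8.3.2 then states: "The above endpoints, other than spontaneous abortion and preterm delivery, are binary and will be analyzed in the same fashion as major structural defects". In practice this means a Fisher or chi-squared test, with logistic regression for adjustment as in section 8.3.1. Neither section mentions an analysis of the measurements or of z-scores.

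Table 3 in section 8.4 gives the SGA row as "SGA Small for Gestational Age 64:106 10% 2.68", with "chi-square test for all other outcomes" in its footnote. It has no row for 1-year size.

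**The concern.** A cut at the 10th percentile treats an infant at the 11th percentile like one at the 90th. If teriflunomide lowers size across the exposed cohort, much of the evidence lies in infants who never cross the cut.

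That matters in this registry because the exposed cohort is small, and section 8.4 says it should not be expected to grow unless pregnancy prevention fails. Using collected data more fully is one of the few ways to gain power. A moderate effect on growth could otherwise be missed and then read as reassuring.

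Adjustment is the second issue. Section 8.3.1 calls confounder adjustment necessary because the study is observational. A logistic model is limited by its number of events, and the cut leaves few. A linear model on the same infants is limited by the number of infants.

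**Working it through.** **Inputs (section 8.4 and Table 3).** "approximately 64 live born infants from a total of 75 enrolled in the teriflunomide-exposed group and 106 live born infants in each comparison group"; loss to follow-up is already inside these counts ("the estimated lost-to-follow-up rate is 4% (based on previous OTIS experience"). Baseline SGA is 10% and the relative risk (RR) is 2.68, so the exposed rate is 26.8%. The standard is "least 80% power and 2-sided significance level of 0.05, under the sample size, except as otherwise noted".

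**1. The plan's own figure.**
- Pooled rate = (64 × 0.268 + 106 × 0.10)/170 = 0.163.
- Standard error under no difference = √[0.163 × 0.837 × (1/64 + 1/106)] = 0.0585.
- Standard error under the alternative = √[0.268 × 0.732/64 + 0.10 × 0.90/106] = 0.0626.
- Power = Φ[(0.168 − 1.96 × 0.0585)/0.0626] = Φ(0.852) = 80.3%.

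Exact enumeration of the uncorrected chi-squared test gives 81.4%. Table 3's entry reproduces.

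**2. The same effect on the z-score scale.** The documents state no model. Assume one normal z-score, equal SD, and every exposed infant shifted by the same amount.
- Shift d = Φ⁻¹(0.268) − Φ⁻¹(0.10) = −0.619 + 1.282 = 0.663 SD.
- Standard error = √(1/64 + 1/106) = 0.158.
- Noncentrality = 0.663/0.158 = 4.19.
- Two-sample t-test power = 98.6%, which is 17.2 points above the exact chi-squared figure.

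At RR 2.0 (20% SGA) the shift is 0.440 SD. The t-test has 78.9% power and the chi-squared test 45.6%. By the normal formula, 80% power needs 0.443 SD, or 20.1% SGA (RR about 2.0 instead of 2.68).

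**3. Any-of-three definition.** Suppose 10% and 26.8% are the rates of being small on any of three measures, with an assumed pairwise correlation of 0.5 to 0.8 and a common shift. One measure analysed on its scale then has 96.3% to 98.0% power.

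**4. Where the gain fails.** The exposed SGA rate is held at 26.8% throughout.

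*Larger spread in the exposed.* With SD ratio r, the mean shift is 1.282 − 0.619r, the standard error is √(r²/64 + 1/106), and power is Φ(shift/SE − 1.96).

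| r | Shift (SD) | Power |
|---|---|---|
| 1.1 | 0.601 | 94.6% |
| 1.2 | 0.539 | 85.4% |
| 1.3 | 0.477 | 71.2% |

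These are unequal-variance figures; at r = 1.3 a pooled-variance t-test has about 75%.

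*Only a fraction π affected, each by D SD.* The mean shift is πD and the exposed variance is 1 + π(1 − π)D².

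| D | π | Power |
|---|---|---|
| 1.0 | 58% | 92.8% |
| 1.5 | 35% | 81.4% |
| 2.0 | 25% | 75.1% |
| 2.5 | 21% | 74.4% |
| 3.0 | 20% | 77.2% |

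A pooled-variance t-test does slightly better, at 79% to 81% with 25% to 30% affected. That is at best level with the chi-squared test.

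**5. Events available for adjustment.**
- No effect: 0.10 × 170 = 17.
- Table 3's alternative: 64 × 0.268 + 106 × 0.10 = 27.8.

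Section 8.2 lists 13 items. The last three (teriflunomide dose and timing, elimination procedure, blood levels) concern exposed women only, so ten can confound Cohort I versus II. With exposure, that is at least 11 parameters: 17/11 = 1.5 to 28/11 = 2.5 events per parameter. Under an assumed rule of 10 events per parameter, 28 events carry exposure plus about one covariate. Under a rule of 5, they carry exposure plus about four. A linear model has 170/11, about 15 infants per parameter.

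**The case against.** The strongest reply is that the plan contains no error. The stated objective is SGA, which is a percentile category by definition, and a chi-squared test with logistic regression answers it. A mean z-score difference is a different quantity. This stands: the named endpoints should remain, and the continuous analysis belongs beside them. The SAP could also add it, since section 8 allows documented differences. Even so, section 8.3.2 positively declares these endpoints binary.

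A reader might infer that the cut costs 17 points of power outright. The documents do not support that, because the figure needs an equal shift in all exposed infants with unchanged spread. Section 6.2.1 admits exposure of any length and dose up to week 12, and section 8.3.2 says the success of elimination influences fetal exposure. Uneven effects are therefore plausible, and step 4 shows that the gain can then vanish or reverse.

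A reader might also carry the figure over to 1-year size. Table 3 gives no rate or effect there, so it cannot be derived.

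Finally, a reader might infer that adjustment is impossible. Section 8.2 says its items may or may not be used. Section 8.3.1 selects confounders by a 10% change in the odds ratio or by clinical relevance, limits stepwise modelling by sample size, and considers propensity scores. A small model or a single propensity-score term remains feasible.

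It is also fair to say that sorting infants at a percentile does not by itself produce z-scores. Section 7.2.3.4 uses NCHS curves for term infants and unspecified prenatal curves for preterm infants, so suitable references have to be named.

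**Conclusion.** The point holds as a modest, inexpensive improvement to secondary endpoints. The protocol analyses size only through a 10th-percentile cut although the measurements are collected.

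For birth SGA at Table 3's effect, power is about 81% with the cut and about 98.6% with a t-test. At RR 2.0 it is 46% against 79%. Both comparisons rest on a normal z-score, equal spread and a uniform shift, none of which the protocol states. With about a quarter of exposed infants affected, or an exposed SD about 1.3 times larger, the continuous test is no better than the cut or is worse. For 1-year size the loss of information applies in principle but has no figure.

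On adjustment, 17 to 28 events are too few for the ten shared confounders together, but enough for a limited model.

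**What to change.** Keep the SGA and postnatal growth deficiency comparisons as the named secondary endpoints. Add to section 8.3.2, and carry into the SAP:

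- A pre-specified linear regression of size z-scores on cohort and confounders, Cohort I versus II first and then versus III.
- At birth, z-scores for gestational age and sex in singletons, matching the exclusion of multiples from SGA in section 8.3.3. At 1 year, z-scores for age and sex, with adjusted age for preterm infants.
- Named references that yield z-scores for both term and preterm infants.
- One lead measure (for example weight), so that testing is not multiplied over three measures.
- Unequal-variance or robust standard errors, with mean differences and 95% confidence intervals.

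The cost is protocol and SAP wording, the choice of references and a few models. No new data, visits or participants are needed. The downside is that a mean z-score difference is less familiar clinically and no more sensitive when only a subgroup is affected. The percentile comparison therefore stays.
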